#### 14.7.1 Events exempt from immediate reporting as SAEs

Hospitalisation for a pre-existing condition, including elective procedures planned prior to study entry, which has not worsened, does not constitute a serious adverse event. A&E attendances should not routinely be reported as SAEs unless they meet the SAE definition described above.

#### 14.8 Expectedness

#### 14.8.1 SAEs

There are no expected serious adverse reactions. All SARs identified as probably, possibly or definitely related will therefore be treated as unexpected and reported as SUSARs.

#### 14.8.2 AESIs

There are no AESIs of special interest as wheeze is a primary study outcome and any hospitalisations will be collected as SAEs.

#### 14.9 SUSAR Reporting

Under direction of the Chief Investigator, all SUSARs will be reported by uMed with support from the sponsor to the relevant Competent Authority and to the REC and other parties as applicable. For fatal and life-threatening SUSARs, this will be done no later than 7 calendar days after the CI, Sponsor or delegate is first aware of the reaction. Any additional relevant information will be reported within 8 calendar days of the initial report. All other SUSARs will be reported within 15 calendar days.

Principal Investigators will be informed of all SUSARs.

#### 14.10 Development Safety Update Reports

A Development Safety Update Report (DSUR) will be prepared by the Sponsor to cover a one year reporting period in line with current UK legislation requirements and the approved safety management plan. This will be submitted to the Competent Authority, Ethics Committee and HRA within 60 calendar days of the defined Data Lock Point (DLP).

#### 14.11 Interim and End of Study reviews

An interim DSMB review (see also section 17.1.2) will be held at 7 days post 100 participants vaccinated, and 14 days post 500 participants vaccinated. Both reviews will be held whilst recruitment continues.

For the second DSMB review after 500 participants have completed their day 14 diary, this will provide >80% power to detect a RR of 6 for medically attended wheeze, assuming the wheeze rate is 0.9% for the placebo. If the DSMB find that there is a significant increase in medically attended wheeze in the vaccine arm, the study can be halted for further discussion and investigation.

The safety profile will be assessed on an on-going basis by the Investigators. The CI and relevant Investigators (as per the trial delegation log) will also review safety issues and SAEs as they arise.

The DSMB will review safety data accumulated when the study is fully recruited. The DSMB may also be consulted should safety concerns arise at any point.

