#### 12.5.3 Safety review

Due to the rapid recruitment and short study period, there are no planned safety reviews whilst the study is ongoing. Safety reviews can be conducted on an ad-hoc basis as requested by the DSMB.

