#### 15 Statistics

#### 15.1 Sample size

The primary objective of this study is to determine the relative risk of medially attended wheezing in 28 days following LAIV vaccination compared with placebo. The null and alternate hypotheses are:

H0: Proportion of wheezing LAIV = Proportion of wheezing Placebo

H1: Proportion of wheezing LAIV ≠ Proportion of wheezing Placebo

Where the proportion of wheezing is calculated as the number of participants with respiratory wheezing diagnosed by a health practitioner requiring medical attention within 28 days following receiving LAIV or a placebo. We chose 28 days as this is the common interval to observe intermediate reactions following vaccination. The study was a cross-over design, i.e. participants randomised to LAIV or placebo at Day0 will receive placebo or LAIV at Day28, respectively. Although there is no data on the ideal washout period, it is biologically reasonable to assume that the impact of LAIV will last shorter than 28 days. The data from a previous publication comparing medically significant wheeze rates between LAIV and inactivated vaccine groups reported 44 vs 20 cases in the first 28 days following vaccination, and 11 vs 14 cases between 29-42 days post-vaccination, further supporting our assumption. Therefore, we will use both Day 0-28 and Day 28-56 periods in the primary analysis in the primary analysis.

The sample size calculation is based on the below assumptions:

- 1. The proportion of medially attended wheezing is 0.9% following placebo in 28 days following vaccination;
- 2. The relative risk of interest is 2;

- 3. Study power of 80%;
- 4. Type I error of 0.05 two-sided;

Based on the above sample size, the study will need to recruit 2800 effective participants. Given the study endpoint will be extracted based on electronic medical records, we expect the attrition rate will be low. The total sample size will be 3000.

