#### 15.3 Interim analyses

There will no formal interim analysis.

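### The >80% power quoted for the DSMB review at 500 participants applies a 28-day placebo rate to a review that guarantees only 14 days of follow-up, and section 12.5.3 says no such review is planned

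*Protocol*

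**What the plan says.** Section 14.11 of the protocol plans two DSMB reviews while recruitment continues: 7 days after 100 participants are vaccinated and 14 days after 500 are vaccinated. The second is introduced as "For the second DSMB review after 500 participants have completed their day 14 diary", and the power statement attached to it is "this will provide >80% power to detect a RR of 6 for medically attended wheeze, assuming the wheeze rate is 0.9% for the placebo". No time window is given for the rate or for the relative risk. The section adds that the study can be halted if the DSMB finds a significant increase in medically attended wheeze in the vaccine arm.

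The 0.9% is defined in one place only, the first sample size assumption in section 15.1: "The proportion of medially attended wheezing is 0.9% following placebo in 28 days following vaccination".

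On whether reviews are planned, section 12.5.3 says "there are no planned safety reviews whilst the study is ongoing" and allows ad hoc ones at the DSMB's request. Section 15.3 says "There will no formal interim analysis". Section 17.1.2 confirms formal DSMB reviews after 100 and 500 participants and at the end of the trial, and refers to 14.11 for the detail. The amendment history shows that the reviews at 100 and 500 were introduced in version 1.1.

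**The concern.** A rate that accrues over 28 days cannot be carried unchanged to a review at which the last-enrolled children have been followed for only 14. Fewer events will have occurred, so the power must be lower unless something else compensates, and the protocol names nothing that does.

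This matters because it is the only review before full recruitment for which the protocol describes a wheeze comparison. The holding rules in section 14.12 concern hospitalisation, death and related life-threatening events, not wheeze. A DSMB told that the review has more than 80% power could give a non-significant result more weight against a six-fold increase than the data would carry. In addition, a reader who starts from section 12.5.3 would conclude that no review is scheduled.

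**Working it through.** **Inputs**
- Review size: 500 participants in total (14.11), randomised 1:1 (section 3), so n = 250 per arm.
- Placebo risk: 0.9% over 28 days (15.1).
- Relative risk: 6 (14.11).
- Two-sided 5% (15.1) and Pearson's chi-squared test (15.2). Section 14.11 states neither for this review, so both are borrowed from the primary analysis.

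**Formula.** For placebo risk p, vaccine risk q = 6p and mean risk m = (p + q)/2:

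power = Φ{ [ (q − p)√n − 1.96√(2m(1 − m)) ] / √( p(1 − p) + q(1 − q) ) }

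Exact power was also found by enumerating the binomial outcomes for Pearson's and Fisher's tests.

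**Step 1: reproduce the plan's figure.** p = 0.009, q = 0.054, m = 0.0315.
- (q − p)√n = 0.045 × 15.81 = 0.7115
- 1.96√(2 × 0.0315 × 0.9685) = 0.4841
- √(0.009 × 0.991 + 0.054 × 0.946) = 0.2450
- power = Φ(0.2274 / 0.2450) = Φ(0.928) = 82.3%

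Exact Pearson gives 87.3% and Fisher 79.8%. The >80% therefore corresponds to the full 28-day rate.

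**Step 2: 14 days of follow-up.** Assume that placebo risk accrues evenly and that the relative risk of 6 holds within the 14 days. Then p = 0.9% × 14/28 = 0.45%, q = 2.7% and m = 1.575%. Expected events are 250 × 0.0045 = 1.1 on placebo and 250 × 0.027 = 6.75 on vaccine.
- (q − p)√n = 0.0225 × 15.81 = 0.3558
- 1.96√(2 × 0.01575 × 0.98425) = 0.3451
- √(0.0045 × 0.9955 + 0.027 × 0.973) = 0.1754
- power = Φ(0.0107 / 0.1754) = Φ(0.061) = 52.4%

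Exact Pearson gives 54.3% and Fisher 38.3%. At this rate 80% power needs about 480 per arm. At 250 per arm it needs a relative risk of about 9.4 by the formula; exact Pearson gives 83.6% at 9, and Fisher 82.1% at 10.

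**Step 3: longer follow-up in earlier enrolees.** Fourteen days is a minimum. Section 10.1.2 gives a trial period of about 3 months and 56 days per child, leaving about 91 − 56 = 35 days to enrol 3000. At uniform accrual the first 500 arrive in 35 × 500/3000 ≈ 6 days, so mean follow-up is about 14 + 3 = 17 days. If they took twice as long, the mean is about 14 + 6 = 20 days.

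| Mean follow-up (days) | Placebo vs vaccine risk | Formula | Exact Pearson | Fisher |
|---|---|---|---|---|
| 14 | 0.45% vs 2.70% | 52% | 54% | 38% |
| 17 | 0.55% vs 3.28% | 61% | 64% | 50% |
| 20 | 0.64% vs 3.86% | 68% | 72% | 60% |
| 24 | 0.77% vs 4.63% | 76% | 81% | 71% |
| 28 | 0.90% vs 5.40% | 82% | 87% | 80% |

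**Step 4: an early vaccine effect.** Suppose instead that the relative risk of 6 is a 28-day contrast, an excess of 5.4% − 0.9% = 4.5 points.
- All of the excess by day 14: 0.45% vs 4.95%, power 88% by the formula, 93% exact Pearson, 88% Fisher.
- Three-quarters of it by day 14: 0.45% vs 3.825%, power 74%, 80% and 69%.

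**Step 5: the sections on planned reviews, side by side.** Sections 14.11 and 17.1.2 schedule reviews at 100 and 500, and 14.11 places both during recruitment. Section 12.5.3 says none is planned while the study is ongoing. These statements cannot all hold. Section 15.3 concerns a formal interim analysis and does not mention DSMB reviews.

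**The case against.** The strongest reply is that the 14-day figure is conditional. The protocol gives no 14-day rate. Follow-up exceeds 14 days for the earlier enrolees, and outcomes also come from GP records, not only from the diary. Section 15.1 expects any vaccine effect to last less than 28 days, so the excess could come early, and step 4 shows that power could then exceed 80%. All of this stands. A reader might infer that power at this review is simply about one half; the documents do not support a single figure. Nor do they support the stated one: 14.11 gives no window for the relative risk, and nothing in the protocol says that the excess falls within 14 days or that mean follow-up will approach 24-28 days.

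A reader might also infer that both 12.5.3 and 15.3 deny the review. Only 12.5.3 does. A DSMB safety review need not be a formal interim analysis, so 15.3 is merely in tension with a review that carries a power statement and a possible halt on a significant increase. Given the amendment history, 12.5.3 looks like text that was not updated.

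The harm should not be overstated either. The protocol does not say that the DSMB will treat a null result as excluding a relative risk of 6, and the final analysis does not depend on this sentence. The hospitalisation, death and life-threatening-event rules and the prompt reporting of respiratory SAEs to the DSMB also remain. The test and significance level for this review may be in the DSMB charter, so their absence here is not a fault.

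**Conclusion.** The point holds as a mismatch between rate and follow-up. The stated >80% matches 250 per arm at the 28-day rate of 0.9%, and the review guarantees only 14 days. With a constant hazard, a relative risk of 6 within the window and a two-sided 5% test, power at 14 days is about 52-54% by Pearson and 38% by Fisher. It is about 61-64% at a mean of 17 days and 68-72% at 20 days (Pearson). Exceeding 80% requires follow-up near 24-28 days or most of the vaccine excess within 14 days, and the protocol states neither. The claim is therefore unsupported as written, though it is not shown to be false under every possible timing of effect.

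The contradiction between 12.5.3 and sections 14.11 and 17.1.2 rests on the text alone and needs no assumption.

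**What to change.** In section 14.11, restate the power on the follow-up available at the second review, and give the window for both the 0.9% and the relative risk of 6. Under a constant hazard at 14 days, that is about 52-54% for a relative risk of 6 by Pearson's test, or about 80% for a relative risk of 9-10. Alternatively, keep the >80% and say that it refers to complete 28-day data on those 500 participants. If an early vaccine effect is the intended justification, state that assumption.

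Reconcile section 12.5.3 with the reviews in 14.11 and 17.1.2, and word 15.3 so that its relation to those reviews is clear.

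These are wording changes only; design and sample size are unaffected. The cost is a less favourable stated power.

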#### 14.12 Safety Holding Rules

The study will be paused if, at any point following the review of the first 500 participants:

- The baseline hospitalisation risk significantly exceeds 2.5%, which is the hospitalisation rate in the previous phase III trial (4), **AND**
- The RR of hospitalisation in the vaccine arm vs the placebo arm becomes greater to a statistically significant degree (p<0.05)

FluSNIFF tridler

Or

 Any death or any life-threatening SAE considered related to the IMP (i.e. that cannot reasonably be attributed to a cause other than vaccination).

The study can be paused upon advice of the DSMB, Chief Investigator, Study Sponsor, regulatory authority, Ethical Committee(s), for any single event or combination of multiple events which, in their professional opinion, jeopardise the safety of the participants or the reliability of the data.

If the trial is halted due to safety concerns, the trial can only be re-started after regulatory authority approval via a substantial amendment.

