## 14.7 Reporting Procedures for Serious Adverse Events

Study sites can be alerted to SAEs via three mechanisms:

• Direct solicitation at follow-up visits.

- Participant reports hospital admission in eDiary (uMed will then notify trial site).
- Participant directly reports SAE to uMed via central telephone number or email on study card (uMed will then notify trial site).

Once the site had been notified of an SAE, the site investigator is required to complete the SAE CRF to notify the Chief investigator or delegate. This may require the investigator to contact the participant's parent/legal guardian to gather information regarding the nature of the SAE. If report of the SAE has come via uMed, they will also notify the CI/delegate of its occurrence so they are aware of a pending report.

In order to comply with current regulations on SAE reporting to regulatory authorities, the event will be documented accurately and notification deadlines respected. SAEs will be reported promptly once the local Investigator/study team becomes aware of their occurrence. Copies of all reports will be forwarded for review to the Chief Investigator (as the Sponsor's representative) or delegate within 24 hours of the Investigator being aware of the suspected SAE. The DSMB will be notified of SAEs that are deemed possibly, probably or definitely related to study interventions; the chair of DSMB will be notified immediately (within 24 hours) of the CI/sponsor being aware of their occurrence. SAEs which are related to a respiratory event will also be reported promptly to the DSMB. SAE will not normally be reported immediately to the ethical committee(s) unless there is a clinically important increase in occurrence rate, an unexpected outcome, or a new event that is likely to affect safety of trial participants, at the discretion of the Chief Investigator and/or DSMB. In addition to the expedited reporting above, the Investigator shall include all SAE in the annual Development Safety Update Report (DSUR) report.

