#### 17 Trial committees

#### 17.1.1 Trial Steering Committee

A Trial Steering Committee will be formed to oversee the study, and advise the Study Management Committee on key issues of study conduct, including, but not limited to, study pauses due to safety concerns on the advice of the DSMB.

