# 28 Appendix B: Amendment History

Amen dment No.	Protocol Version No.	Date issued	Author(s) of changes	Details of Changes made
1	1.1	14th Aug 2025	[name]	
 
Clarified global end of trial defined as LVLS (section 7).
 
Amended exclusion criteria to include receipt of salicylate therapy, and receipt of an IMP within 12 weeks or five half-lives of the IMP (whichever is longer) prior to the first study dose (section 11.3).
 
The ability for investigators to immediately unblind a participant, where considered necessary, has been clarified (section 12.4).
 
Introduction of a DSMB review at 7 days post 100 participants vaccinated and 14 days post 500 participants vaccinated (section 14.11)
 
Introduction of holding rules for baseline hospitalization rate >2.5% and significant increased hospitalizations in vaccination group (p<0.05), OR a fatal/life threatening SAE considered associated with the IMP (section 14.12)
 
Clarified that in the event the study is paused for safety concerns, that a substantial amendment would be required prior to restarting (section 14.12).
 
Recommended site visit for safety assessment where clinically indicated for review of medically attended adverse events thought possibly related to the IMP (section 14.5).
 

		•	Amend references to placebo to clarify this
			is routine NHS stock normal saline stored at
			study sites.

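### Section 14.12 contains no mandatory pause for a related death or life-threatening SAE before the review of the first 500 participants

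*Protocol*

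**What the plan says.** Section 14.12 (Safety Holding Rules) opens with "The study will be paused if, at any point following the review of the first 500 participants". Under that clause stand two conditions joined by AND: a baseline hospitalisation risk significantly above 2.5%, and a significantly raised relative risk of hospitalisation in the vaccine arm. Then comes *Or* on its own line, followed by "Any death or any life-threatening SAE considered related to the IMP (i.e. that cannot reasonably be attributed to a cause other than vaccination".

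The next sentence of 14.12 gives a general power with no start time: "The study can be paused upon advice of the DSMB, Chief Investigator, Study Sponsor, regulatory authority, Ethical Committee(s), for any single event". That power is permissive.

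Other provisions apply from the first dose:

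- Section 14.7, on related SAEs: "the chair of DSMB will be notified immediately (within 24 hours) of the CI/sponsor being aware of their occurrence".
- Section 14.8.1: "All SARs identified as probably, possibly or definitely related will therefore be treated as unexpected and reported as SUSARs".
- Section 14.9: fatal or life-threatening SUSARs go to the authority within 7 calendar days.
- Section 17.1.2: the DSMB may recommend a hold after a related SAE, and its recommendations go to the Trial Steering Committee.
- Section 17.1.1: that committee's role is to "advise the Study Management Committee on key issues of study conduct, including, but not limited to, study pauses due to safety concerns".

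Section 14.11 schedules DSMB reviews 7 days after 100 participants and 14 days after 500 participants are vaccinated, and adds: "Both reviews will be held whilst recruitment continues".

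**The concern.** A start after 500 participants suits the hospitalisation rule, which compares rates and needs accumulated data. It does not suit a trigger that a single event should trip. A related death or life-threatening SAE is the case in which a holding rule should leave least to interpretation, and as worded the mandatory rule does not reach that event in the first 500 children.

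Before the review, a pause depends on someone advising it. The protocol sets deadlines for notification but none for deciding to pause. If the advice comes from the DSMB, it passes through the Trial Steering Committee. Whether a pause is automatic also has formal consequences, because 14.12 requires regulatory approval through a substantial amendment before restart after a safety halt. Sites, sponsor and DSMB should not be able to reach different answers from the same list.

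**Working it through.** **The wording.** The question is whether any text supplies both a mandatory verb and a start at the first dose for this event.

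| Provision | Mandatory pause? | In force from first dose? |
|---|---|---|
| 14.12, opening clause with the hospitalisation pair | Yes | No, after the 500 review |
| 14.12, death/life-threatening item read under the opening clause | Yes | No, after the 500 review |
| 14.12, the same item read as detached | No, it has no verb | No timing given |
| 14.12, general power to pause on advice | No, permissive | Yes |
| 14.7 and 17.1.2, DSMB notification within 24 hours | No, notification only | Yes |
| 14.8.1 and 14.9, SUSAR handling and 7-day report | No, reporting only | Yes |
| 17.1.2, DSMB recommendation to hold | No, permissive | Yes |
| 14.11, review after 100 participants | No pause rule attached | After 100 participants |
| 20.3, Urgent Safety Measures | No, an allowance to act | Yes |

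No row has *yes* in both columns. The page layout of 14.12 is not preserved in the text available, but indentation could only show whether the item belongs under the opening clause. Neither position gives it both properties.

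**Number of children dosed before the mandatory rule starts.**

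- Inputs: 3000 children in total and 1:1 allocation (section 3, Protocol Summary); 1500 children given vaccine first (section 4); rule start after the review of the first 500 (14.12).
- Share of all children: 500 / 3000 = 16.7%.
- Given LAIV at Day 0: 500 / 2 = about 250, and 250 / 1500 = 16.7% of the early-vaccine arm.
- Children enrolled between the 500th vaccination and the completed review come on top. No accrual rate is given, so no figure is put on them.

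**The plan's own figure for that review.** Section 14.11 claims more than 80% power for a relative risk of 6 with 0.9% wheeze on placebo. Taking 0.9% as given, the vaccine rate is 6 × 0.9% = 5.4%. With 250 per arm and two-sided alpha 0.05 (stated in 15.1 for the main analysis and assumed here), the normal approximation gives 82.3%, which reproduces the claim. Exact enumeration gives 87.3% for the uncorrected chi-squared test and 79.8% for Fisher's exact test. The wording point does not depend on this figure.

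**The case against.** The strongest counter-argument is a third reading: the instruction to pause governs both alternatives, and the post-500 timing belongs only to the hospitalisation pair. The item does sit under the heading on holding rules, *Or* stands apart from the AND-joined pair, and the permissive sentence comes separately afterwards. The amendment history also lists the trigger among the holding rules with no start time: "OR a fatal/life threatening SAE considered associated with the IMP (section 14.12". This may well be what was meant. But the reading has to keep the verb of the opening clause and drop the timing phrase that stands before the same colon, which the sentence does not allow. The amendment entry gives no start time for the hospitalisation rule either, so it is weak evidence of intent, and it is used here for nothing more.

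The second argument is that early protection is substantial. This stands. The Chief Investigator or sponsor can advise a pause without the committee route, SAEs are reviewed as they arise, and Urgent Safety Measures are available. These provisions limit the seriousness of the gap but do not make the pause mandatory. The statement that recruitment continues concerns the scheduled reviews and does not describe the response to a related death.

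Third, a mandatory trigger still rests on a judgement of relatedness. That is true, although 14.5 already asks the reporting investigator to assign causality at once. The correction removes the uncertainty about timing and obligation, not the clinical judgement. The DSMB charter and safety management plan are not available and may say more, but the holding rule in the protocol should be clear without them.

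**Conclusion.** The concern holds. As written, 14.12 imposes no mandatory pause for a related death or life-threatening SAE until the 500-participant review. The window covers at least 16.7% of participants, including about 250 LAIV recipients at Day 0, plus an unquantified number enrolled up to the review. The protocol gives no rate for such events, so no expected harm is claimed.

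The claim is limited: the trial can be paused at any time, but before the review nothing says that it must be. No estimate, power calculation or analysis is affected. It should be corrected because it concerns a stated safety rule and costs almost nothing to put right. Confidence is medium, because the wording is loose and the intent was probably broader than the text.

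**What to change.** Split 14.12 into two rules.

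1. Single-event rule, for example: *From the first dose onwards, the study will be paused if a death or life-threatening SAE judged related to the IMP occurs.* Keep the existing bracketed explanation of relatedness.
2. Hospitalisation rule: keep the present opening clause, with its start after the 500-participant review, for the two AND-joined conditions only.

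As a separate correction, amend 12.5.3. It states that no safety reviews are planned during the study, whereas 14.11 and 17.1.2 plan DSMB reviews after 100 and 500 participants, and the start of the hospitalisation rule depends on the second of these.

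The cost is one added sentence and one corrected sentence, with no extra participants, visits or data.

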## 10.1.5 Late Vaccine (LV)

Participants randomised to LV will receive 0.2ml of 0.9% saline placebo nasal spray on day 0 (0.1ml per nostril). At the follow up visit on day 28 they will receive the study intervention of 0.2ml Fluenz nasal spray (0.1ml per nostril). Their final follow up visit will be on day 56 post randomisation.

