#### 17.1.2 Data Safety Monitoring Board

A Data Safety Monitoring Board (DSMB) will be convened. The DSMB will evaluate frequency of events, safety and efficacy data as specified in the DSMB charter. The DSMB will make recommendations concerning the conduct, continuation or modification of the study for safety reasons to the Trial Steering Committee.

The DSMB will review SAEs deemed possibly, probably or definitively related to study interventions. The DSMB will be notified within 24 hours of the CI/Sponsor being aware of their occurrence. The DSMB can recommend placing the study or specific arms of the study on hold if deemed necessary following a study intervention-related SAE.

DSMB formal reviews after 100 and 500 participants and at the end of the trial are detailed in section 14.11.

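### The mandatory hospitalisation pause also requires an undefined 'baseline' risk significantly above a historical 2.5%, so a significant vaccine excess need not force a pause

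*Protocol*

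**What the plan says.** Section 14.12 opens with a mandatory rule: "The study will be paused if, at any point following the review of the first 500 participants", two hospitalisation conditions are met. The first is "The baseline hospitalisation risk significantly exceeds 2.5%, which is the hospitalisation rate in the previous phase III trial". The second is "The RR of hospitalisation in the vaccine arm vs the placebo arm becomes greater to a statistically significant degree (p<0.05". They are joined by an emphasised AND. The only alternative mandatory trigger is a death or life-threatening SAE considered related to the vaccine.

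The protocol does not say whether baseline risk refers to the placebo arm or to both arms together. It gives no follow-up window for the 2.5%, no test for the first condition, and no expected hospitalisation rate for this trial.

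Other routes to a pause are permissive. Section 14.12 adds "The study can be paused upon advice of the DSMB, Chief Investigator, Study Sponsor", as well as the regulator or ethics committees. Section 14.11 says "If the DSMB find that there is a significant increase in medically attended wheeze in the vaccine arm, the study can be halted". Section 17.1.2 says "The DSMB can recommend placing the study or specific arms of the study on hold if deemed necessary" after a related SAE. Section 14.7 adds that "SAEs which are related to a respiratory event will also be reported promptly to the DSMB".

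**The concern.** The second condition is the one that shows harm from the vaccine. Because of the AND it is not enough: the level of hospitalisation must also be significantly above a figure taken from another trial. If hospitalisation here is rarer than 2.5% over the period counted, a clear vaccine excess can meet the second condition and still force nothing. If the 2.5% was measured over more than 28 days, the like-for-like 28-day rate would be lower, which makes this more likely. The protocol does not say.

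This is the protocol's only pre-set between-arm trigger for hospitalisation. It also matters for children still to be dosed. For the late group, section 10.1.5 says "At the follow up visit on day 28 they will receive the study intervention of 0.2ml Fluenz nasal spray". When 28-day data are complete for the first n children per arm, at most about 1500 - n late-group doses remain: 1000 at n = 500 and 500 at n = 1000. Those counts allow nothing for reporting or decision time, so they are upper limits.

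**Working it through.** **The plan's nearest figure.** Section 14.12 states no operating characteristics. Section 14.11 claims more than 80% power for a wheeze RR of 6 at 0.9% placebo with 500 children (250 per arm). With p0 = 0.009, p1 = 0.054 and mean 0.0315:

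power = Φ[(0.045×√250 - 1.96×√(2×0.0315×0.9685)) / √(0.009×0.991 + 0.054×0.946)] = Φ[(0.7115 - 0.4841)/0.2450] = Φ(0.93) = 0.82.

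That claim reproduces. It concerns wheeze and says nothing about the hospitalisation rule.

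**Set-up for the rule.** From the protocol: 1:1 allocation, 2.5%, p<0.05. Assumed: first-period comparison, complete 28-day data, looks at 250, 500 and 1000 per arm, background rates of 1% to 3%. With x placebo and y vaccine hospitalisations among n per arm:

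- RR condition: z = ((y - x)/n) / √(2p̄(1 - p̄)/n) > 1.96, where p̄ = (x + y)/2n.
- Baseline condition, test version: exact one-sided binomial test against 2.5% at the 5% level, on x (placebo reading) or x + y (pooled reading).
- Baseline condition, observed version: the observed rate simply exceeds 2.5%.

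The chance of firing is the sum of Bin(x; n, p0) × Bin(y; n, p1) over all (x, y) that meet both conditions.

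**Counts needed (actual size of the test).** Placebo reading: 12/250 (0.025), 19/500 (0.050), 34/1000 (0.048), 49/1500 (0.039). Pooled reading: 19/500 (0.050), 34/1000 (0.048), 63/2000 (0.040), 90/3000 (0.048).

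**Placebo reading, test version.** P(pause) ≤ P(baseline condition met). At a true placebo rate of 2.5% or less this cannot exceed the sizes above, about 2.5-5% per look, for any RR. The limit is per look: at 2.5% and RR 4 the chance accumulates to 9.0% over four looks (250, 500, 750, 1000 per arm).

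**Chance of firing at one look (%), at 250 / 500 / 1000 per arm.**

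| Placebo vs vaccine | RR test alone | Placebo, test | Pooled, test | Pooled, observed |
|---|---|---|---|---|
| 1% vs 3% | 35 / 64 / 91 | 0 / 0 / 0 | 0.4 / 0.2 / 0.04 | 11 / 9 / 5 |
| 1% vs 4% | 60 / 89 / 99.5 | 0 / 0 / 0 | 4 / 5 / 4 | 35 / 42 / 46 |
| 1% vs 6% | 91 / 99.7 / 100 | 0 / 0 / 0 | 38 / 59 / 82 | 83 / 95 / 99 |
| 1.5% vs 4.5% | 52 / 82 / 98 | 0 / 0 / 0 | 12 / 23 / 36 | 43 / 67 / 88 |
| 2% vs 4% | 26 / 46 / 76 | 0 / 0 / 0.01 | 6 / 14 / 29 | 21 / 39 / 69 |
| 2.5% vs 5% | 31 / 55 / 85 | 0 / 0.2 / 1.4 | 18 / 43 / 79 | 30 / 55 / 84 |
| 2.5% vs 7.5% | 75 / 96 / 100 | 0.3 / 3 / 5 | 70 / 96 / 100 | 75 / 96 / 100 |
| 3% vs 6% | 36 / 63 / 91 | 0.1 / 3 / 18 | 31 / 62 / 91 | 36 / 63 / 91 |

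Placebo reading, observed version: at most about 1% in the 1% and 1.5% rows and 3% in the 2% vs 4% row, but 6 / 15 / 11% at 2% vs 6% and 23 / 45 / 45% at 2.5% vs 7.5%.

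**One concrete case.** Take 30 vaccine and 10 placebo hospitalisations at 1000 per arm: z = 0.02/√(2×0.02×0.98/1000) = 3.19, two-sided p = 0.001. The test version needs 34 placebo events (10 seen) or 63 pooled (40 seen). The observed rates are 1.0% and 40/2000 = 2.0%. No reading forces a pause.

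**False pauses.** With no true effect, at rates of 1-2.5% and four looks (simulated), the RR test alone pauses in the harm direction in 6.0-6.4% of trials at p<0.05 and 0.9-1.2% at p<0.01. The present rule, pooled test version at 2.5%, gives 0.35%. For 1% vs 3% over four looks, firing is 93% at p<0.05, 78% at p<0.01 and 0.6% under the present pooled test version.

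**The case against.** The AND is emphasised, and the amendment history joins the same two conditions, so it looks intended. Requiring an absolute as well as a relative excess guards against pausing on a handful of events, and section 14.12 makes a restart after a safety halt depend on a substantial amendment. In a trial of about three months that cost is real. This stands as a reason for some guard. It does not make a historical-rate condition the right one, since a stricter p-value limits false pauses at much less cost in sensitivity.

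The low background rates are assumptions. The only hospitalisation figure in the protocol is 2.5%, and section 12.1.1 enriches recruitment for children prone to wheeze. This also stands: on the pooled reading at 2.5% or above, little is lost for RR 3. The pooled results depend on the unstated test too, as the last two columns show, so no fixed excess, such as fourfold, can be given as the point below which the rule is silent. The four-look schedule is likewise assumed.

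A reader might infer that the trial has no protection against excess hospitalisation, or that the rule can never fire. The documents support neither. The discretionary routes, DSMB reporting and the mandatory pause for a related death or life-threatening SAE all remain, and the DSMB charter, which is not at hand, may define terms. But for hospitalisation in general those protocol routes permit a pause and do not require one.

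**Conclusion.** The point holds for this one mandatory rule. On the placebo reading with a one-sided 5% test, the rule is close to inoperative at any true placebo rate up to its own 2.5% reference, and this needs no assumption about the background rate. On the pooled reading the loss is severe at an assumed 1% vs 3% under either version of the first condition. At 1.5-2% it ranges from modest to large, depending on the test and the RR. At 2.5% with a 5% test it is small for RR 3 and moderate for RR 2 (18% against 31% at 250 per arm, 43% against 55% at 500). Above 2.5% it is small. Defining baseline as pooled would therefore not repair the rule at low rates. It should be fixed. Confidence is medium, because the true hospitalisation rate and the intended test are not stated.

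**What to change.** Amend section 14.12 so that a significant between-arm hospitalisation comparison is sufficient by itself at pre-set looks. Move the 2.5% criterion to a separate trigger for DSMB review, stating its arm, follow-up window and test. Use a stricter boundary such as p<0.01 and give the DSMB a short table of firing and false-pause chances at several background rates and RRs, so that it and the sponsor can settle the boundary.

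The cost is amendment wording and that table. At p<0.01 sensitivity for 1% vs 3% falls from 93% to 78% over four assumed looks, and at a single look to 12%, 37% and 75% at 250, 500 and 1000 per arm. False pauses would be about 1% over four looks, slightly more than under the present rule but well below the roughly 6% at p<0.05.
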